6.2 IMPORTANT PROTOCOL DEVIATIONS

Consistency check listings (for identification of deviations from time windows) and a list of protocol deviations (e.g. deviations in drug administration, in blood sampling times, etc.) will be provided to be discussed at the Report Planning Meeting. At this meeting, it will be decided whether a discrepant data value can be used in analyses, must be corrected in the clinical database or constitutes a PD.

Each protocol deviation must be assessed to determine whether it is an important PD (IPD). For definition of IPDs, and for the process of identification of these, refer to the BI reference document "Identify and Manage Important Protocol Deviations (IPD)" [\(2\)](#).

If any IPDs are identified, they are to be summarised into categories and will be captured in the decision log. Categories which are considered to be IPDs in this trial are defined in the DV domain template. If the data show other IPDs, the definition in the DV domain template will be supplemented accordingly by the time of the Report Planning Meeting.

CTP Section 7.2.1: *Important protocol deviations (IPD) categories will be suggested in the IQRMP and specified in more detail in the TSAP, IPDs will be identified no later than in the Report Planning Meeting, and the IPD categories will be updated as needed.*

IPDs will be summarized and listed. Which kind of IPDs could potentially lead to exclusion from which analysis set is specified in the DV domain template. The decision on exclusion of subjects from analysis sets will be made at the latest at the Report Planning Meeting, after discussion of exceptional cases and implications for analyses. If the data show other IPDs, this table will be supplemented accordingly by the time of the Report Planning Meeting.

Non-important COVID-19 related PDs will only be listed.

6.3 SUBJECT SETS ANALYSED

Subject sets will be used as defined in Section 7.2.1 of the CTP:

- **Treated set (TS):**
The treated set includes all subjects who were randomized and treated with at least one dose of study drug or ketamine. The treated set will be used for safety analyses.
- **Pharmacodynamic set (PDS):**
PD analyses will be based on the PDS which is defined as all randomised patients who performed the post ketamine tests in at least one period.

The following additional subject sets will be used:

- **Screened set (SCS):**
This set includes all subjects who signed the informed consent form.

[figure not shown]

Table 6.3: 1 Subject sets analysed

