7.2.5 Safety analyses

Adverse events will be coded using the Medical Dictionary for Drug Regulatory Activities (MedDRA). Standard BI summary tables and listings will be produced. All adverse events with an onset between start of treatment and end of the REP, a period of 11 days after the last dose of randomised trial medication, will be assigned to the on-treatment period for evaluation.

The safety analysis will be done by 'treatment at onset'.

All treated patients will be included in the safety analysis. In general, safety analyses will be descriptive in nature and will be based on BI standards. No hypothesis testing is planned.

Statistical analysis and reporting of adverse events will concentrate on treatment-emergent adverse events, i.e. all adverse events occurring between start of treatment and end of the REP. Adverse events that start before first drug intake and deteriorate under treatment will also be considered as 'treatment-emergent'.

Frequency, severity, and causal relationship of adverse events will be tabulated by system organ class and preferred term after coding according to the current version of the Medical Dictionary for Drug Regulatory Activities (MedDRA) at database lock.

Vital signs, physical examinations, or other safety-relevant data observed at screening, baseline, during the course of the trial and at the end-of-trial evaluation will be assessed with regard to possible changes compared to findings before start of treatment.

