6. GENERAL ANALYSIS DEFINITIONS

6.1 TREATMENTS

For basic study information on treatments to be administered, assignment of treatment groups, and selection of doses, cf. Section 4 of the CTP.

Each subject is planned to be treated in three subsequent treatment periods with one single dose at Day 1 in each treatment period:

- Test treatment 1 (T1):
300 mg of Lamotrigine as tablet
- Test treatment 2 (T2):
[REDACTED] of BI 409306 as film-coated tablet
- Test treatment 3 (T3):
[REDACTED] of BI 425809 as film-coated tablet
- Reference treatment (R):
Placebo as film-coated tablet

Each subject is planned to be randomly allocated to one of 18 3-period sequences including placebo in one of the periods and 2 out of 3 active treatments in the remaining periods:

T1–T2–R, T1–R–T2, T1–T3–R, T1–R–T3, T2–T1–R, T2–R–T1, T2–T3–R, T2–R–T3, T3–R–T1, T3–T1–R, T3–T2–R, T3–R–T2, R–T1–T2, R–T2–T1, R–T1–T3, R–T3–T1, R–T2–T3, R–T3–T2.

Each treatment period is separated by a washout period of at least 11 days.

[REDACTED] : *The Residual Effect Period (REP)* [REDACTED]
[REDACTED], for lamotrigine 10 days, and for ketamine 24 hours. This is the period
after the last dose with measurable drug levels and/or pharmacodynamic effects is still likely
to be present.

For statistical analyses of AEs and vital signs, the following separate analysis phases will be defined for each subject:

Table 6.1: 1 Analysis phases for statistical analysis of AEs and actual treatment for analysis of vital signs

Study analysis phase	Label of analysing treatment	Label of actual treatment	Start	End
Screening	Screening	Screening	Date of informed consent	Start date/time of screening ketamine infusion
		Screening+Ketamine	Start date/time of screening ketamine infusion	End date/time of screening ketamine infusion + 24 h
		Screening	End date/time of screening ketamine infusion + 24 h	Start date/time of first administration of study treatment (Planned time: 00:00h) in the respective treatment period
On treatment ^{1, 2, 3}	Placebo, [REDACTED] BI 409306, BI 425809 or 300mg Lamotrigine, respectively	Placebo, [REDACTED] BI 409306, BI 425809 or 300mg Lamotrigine, respectively	Start date/time of administration of the first study treatment (Planned time: 00:00h) in the respective treatment period	Start date/time of on-treatment ketamine infusion or 12:00 a.m. on day after subject's trial completion date, whatever comes first

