	Placebo+Ketamine, [REDACTED] BI 409306+Ketamine, [REDACTED] BI 425809+Ketamine or 300mg Lamotrigine+Ketamine, respectively	Start date/time of on-treatment ketamine infusion	End date/time of on-treatment ketamine infusion + 24 h or 12:00 a.m. on day after subject's trial completion date, whatever comes first	
	Placebo, [REDACTED] BI 409306, BI 425809 or 300mg Lamotrigine, respectively	End date/time of on-treatment ketamine infusion + 24 h	Start date/time of administration of the second study treatment (Planned time: 03:00h) in the respective treatment period + 11 days * 24 h/day (for BI 409306, BI 425809, lamotrigine and placebo) or Date/time of administration of study drug in the next treatment period or 12:00 a.m. on day after subject's trial completion date, whatever comes first	
Follow-up	F/U Placebo, F/U [REDACTED] BI 409306, F/U [REDACTED] BI 425809 or F/U 300mg Lamotrigine, respectively	F/U Placebo, F/U [REDACTED] BI 409306, F/U [REDACTED] BI 425809 or F/U 300mg Lamotrigine, respectively	Start date/time of administration of the second study treatment (Planned time: 03:00h) in the respective treatment period + 11 days * 24 h/day (for BI 409306, BI 425809, lamotrigine and placebo)	Date/time of administration of the respective treatment in the next treatment period, if applicable, or 12:00 a.m. on day after subject's trial completion date, whatever comes first.

¹ See [Section 6.7](#) for definition of baseline, which will be used in the statistical analyses of vital signs.

² A REP of 11 days will be used for all study treatments (BI 409306, BI 425809, lamotrigine and placebo) to avoid any bias which might occur due to different observation times. This may lead to an overestimation of AEs in the treatment periods in which subjects received a study treatment with considerably lower REP.

³ The on-treatment phase extends from Day 1 00:00h (planned time) to Day 11 03:00h (planned time) to include AEs which occur after the start of the first study drug (or corresponding placebo) administration (which is not necessarily the analysing treatment of the respective treatment period) as well as AEs which occur within the REP of the second study drug (or corresponding placebo).

Analysis phases for statistical analysis of AEs are defined for each subject as described in [Table 6.1: 1](#).

AE summary tables will present results for the on-treatment phase only. All AEs will be listed.

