In AE tables in CTR Section 15.3 (but not in displays for ClinicalTrials.gov) the following total will be provided in addition:

- **"Total on-trt"**, defined as the total over all on-treatment phases

Listings of AEs presented in Section 15.4 will display results for the screening, on-treatment and follow-up phases (labelled with the name of the study treatment (short label)).

AE tables and listings will be displayed by analysing treatment. Beyond that, listings will include an additional column for the actual treatment (defined in Table 6.1: 1).

Vital signs, ECG, CANTAB, [REDACTED] will be analysed based on the respective treatment (Placebo, BI 409306, BI 425809 or Lamotrigine) with clear differentiation between baseline (cf. [Section 6.7](#)) and post-baseline measurements. Measurements will be considered on-treatment, if they were taken within the on-treatment phases as defined in Table 6.1: 1. ECG measurements are considered to be on-treatment if they were measured between the first administration of the respective treatment and the corresponding residual effect period after the last administration of the respective treatment.

Vital signs listings will include an additional column for the actual treatment (defined in Table 6.1: 1).

More details on the technical implementation of these analyses are provided in the ADS Plan of this TSAP.

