7.8 SAFETY ANALYSIS

All safety analyses for BI 409306, BI 425809, lamotrigine and ketamine will be performed on the TS.

CTP Section 7.2.5: “*The safety analysis will be done by ‘treatment at onset’.*”

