7.8.1 Adverse Events

AEs will be coded with the most recent version of MedDRA.

The analyses of AEs will be descriptive in nature. All analyses of AEs will be based on the number of subjects with AEs and not on the number of AEs.

For further details on summarization of AE data, please refer to "Analysis and Presentation of Adverse Event Data from Clinical Trials" [\(7\)](#) and "Handling of missing and incomplete AE dates" [\(3\)](#).

All AEs will be assigned to the screening, on-treatment or follow-up phase as defined in [Section 6.1](#). AEs will be analysed based on treatments as actually received, defined in [Table 6.1: 1](#).

CTP Section 7.2.5: “Statistical analysis and reporting of adverse events will concentrate on treatment-emergent adverse events, i.e. all adverse events occurring between start of treatment and end of the REP. Adverse events that start before first drug intake and deteriorate under treatment will also be considered as ‘treatment-emergent’.”

The longest REP, i.e. 11 days will be taken for all study treatments (Placebo, BI 409306, BI 425809 and Lamotrigine) to avoid any bias which might occur due to different observation times. This may lead to an overestimation of AEs in the treatment periods in which subjects received a study treatment with considerably lower REP.

An overall summary of AEs will be presented. This overall summary will comprise summary statistics for the class of AESIs.

CTP Section 5.2.6.1.4: *The following are considered as AESIs:*

- *Hepatic injury*
A hepatic injury is defined by the following alterations of hepatic laboratory parameters:
 - *An elevation of AST (aspartate transaminase) and/or ALT (alanine transaminase) ≥ 3 fold ULN combined with an elevation of total bilirubin ≥ 2 fold ULN measured in the same blood sample, or*
 - *Aminotransferase (ALT, and/or AST) elevations ≥ 10 fold ULN*

The investigator had to classify on the eCRF whether an observed AE was an AESI or not.

According to ICH E3 (8), in addition to Deaths and Serious Adverse Events, ‘other significant’ AEs need to be listed in the clinical trial report. These will be any non-serious adverse event that led to an action taken with study drug (e.g. discontinuation or dose reduced or interrupted).

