The frequency of subjects with AEs will be summarised by treatment, primary SOC and preferred term. AEs will also be summarized by maximum intensity. AEs which were considered by the investigator to be drug related will be presented separately. Separate tables will also be provided for subjects with SAEs, related SAEs and subjects with AESIs.

The SOCs and preferred terms within SOCs will be sorted by descending frequency over all treatment groups.

For disclosure of AE data on ClinicalTrials.gov, the frequency of subjects with non-serious AEs occurring with an incidence of greater than 5 % (in preferred terms) will be summarised by treatment, primary SOC and preferred term. The frequency of subjects with SAEs will also be summarised.

For disclosure of AE data in the EudraCT register, the frequency of AEs, the frequency of non-serious AEs with an incidence of greater than 5 % (in preferred terms) and the frequency of SAEs will be summarized.

For support of lay summaries, the frequency of subjects with drug-related SAEs will be summarized by treatment, primary SOC and preferred term.

All AEs occurring in screening, on-treatment and follow-up phase will be listed.

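### On the visible text, adverse events from the Visit 2 ketamine challenge are listed but, with one narrow exception, enter no planned incidence summary

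*SAP*

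**What the plan says.** **Subject set.** Protocol 7.2.1 and SAP 6.3 use the same definition: "The treated set includes all subjects who were randomized and treated with at least one dose of study drug or ketamine". SAP 7.8 then says: "All safety analyses for BI 409306, BI 425809, lamotrigine and ketamine will be performed on the TS". Protocol 7.2.5 adds: "All treated patients will be included in the safety analysis".

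**Analysis phases.** In SAP Table 6.1: 1 the Screening phase contains a window whose actual-treatment label is *Screening+Ketamine*. It runs from the start of the Visit 2 infusion to "End date/time of screening ketamine infusion + 24 h". The analysing-treatment label for that window is simply *Screening*.

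**Outputs.** SAP 6.1 is explicit: "AE summary tables will present results for the on-treatment phase only". Tables are built by analysing treatment, and the one additional total is taken over the on-treatment phases. Actual treatment appears as an extra column in listings only. On listings the SAP says: "Listings of AEs presented in Section 15.4 will display results for the screening, on-treatment and follow-up phases". SAP 7.8.1 repeats it: "All AEs occurring in screening, on-treatment and follow-up phase will be listed".

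**Exception.** Protocol 7.2.5, cited in SAP 7.8.1, has one route from screening into the tables: "Adverse events that start before first drug intake and deteriorate under treatment will also be considered as" treatment-emergent.

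**Purpose.** Protocol 2.2.2.3 names ketamine, alongside the three study drugs, among the agents whose safety and tolerability are to be assessed.

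**The concern.** Visit 2 is each subject's first ketamine exposure in the trial, and it is given with no study drug at all. The only other infusion without an active study drug is in the placebo period. Visit 2 also acts as a filter: under Protocol 3.1 and exclusion criterion 25, subjects whose PALTEA28 score changes by fewer than 10 errors do not continue.

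The tabulated ketamine experience therefore comes only from subjects selected on their Visit 2 response, and only from their later infusions. A reader of the trial report who wants to know how many exposed subjects had an event after the Visit 2 challenge would have to count from a listing, with no denominator supplied. What is at stake is how complete the ketamine safety summary is, not the comparison between treatments.

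**Working it through.** No stated figure is in dispute. The check traces a Visit 2 AE through the plan and then counts infusions.

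**Step 1: order of events.** Protocol 4.1.4 has all subjects undergo the ketamine challenge at screening. Protocol 3.1 then removes non-responders. Protocol 4.1.3 allocates the treatment sequence on the morning of Day 1 of Visit 3. So some subjects can receive ketamine and never be randomised.

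**Step 2: exposed, not randomised.** The Treated Set requires randomisation, so these subjects are outside it. Because SAP 7.8 puts the ketamine safety analyses on that set, they enter none of them. Their events also belong to the Screening phase, so they are excluded by phase as well as by set.

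**Step 3: randomised.** These subjects are in the Treated Set. Their Visit 2 events still fall in the Screening phase, which the AE tables do not cover. For this group the restriction in SAP 6.1 is what matters, not the set definition.

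**Step 4: possible ways back in.**
- A Visit 2 event that worsens under study treatment is counted, but under that study treatment and not as a Visit 2 event.
- SAP 7.8.1 says AEs are analysed by the treatment actually received, as defined in Table 6.1: 1, and *Screening+Ketamine* is one of those labels. The more specific text in SAP 6.1 (on-treatment phase only, tables by analysing treatment) closes this route, although the two statements should be reconciled.

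**Step 5: are the data collected?** Yes. Protocol 5.2.6.2.1 exempts from CRF entry only screening failures that occur before any trial medication or ketamine. Protocol 3.3.4, repeated in SAP 6.6, is less complete. It covers leaving before trial medication or ketamine, and leaving after trial medication, but not leaving after ketamine alone.

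**Step 6: counts.** As a check on the design figures, 36 subjects / 18 sequences = 2 per sequence. Each active treatment appears in 12 of the 18 sequences, so 12 × 2 = 24. Placebo appears in all 18, so 18 × 2 = 36. Both match the synopsis.

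| Infusions in the 36 planned randomised subjects | Number |
|---|---|
| Visit 2 | 36 × 1 = 36 |
| Treatment periods | 36 × 3 = 108 |
| Total | 36 + 108 = 144 |
| Without an active study drug (Visit 2 + placebo period) | 36 + 36 = 72 |

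Share not covered by an AE table: 36 / 144 = 1 in 4 of all infusions, and 36 / 72 = 1 in 2 of those without an active study drug. The documents give no pass rate for Visit 2, so no corresponding share is calculated for subjects who are not randomised.

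**The case against.** The strongest reply is that this is a declared choice. The SAP states the on-treatment restriction openly, the protocol says AE analysis will concentrate on treatment-emergent events, ketamine is a challenge agent, and the main objective concerns the other three drugs. Visit 2 events are collected and listed with an actual-treatment column, disposition is reported on the Screened Set, and SAEs go to the sponsor within 24 hours. Much of this stands: the data are retained, and the extra table is an improvement rather than the repair of an error.

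Three further points also stand.

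- **No direct contradiction.** A reader might infer that the plan breaks its own promise to assess ketamine safety, or to include all treated subjects. The documents do not support that. Protocol 2.2.2.3 promises no incidence table per visit, and the sentence in Protocol 7.2.5 can be read as referring to the Treated Set.
- **Infusions are not the unit of analysis.** SAP 7.8.1 counts subjects with events, and every randomised subject who starts study treatment is covered by the on-treatment tables. Those tables also pool the ketamine window with the rest of the on-treatment phase, so no planned table isolates ketamine events at any visit. The 1-in-4 figure describes infusions covered; it is not a share of ketamine AE incidence lost.
- **Part of the SAP is not visible.** SAP 6.3 announces additional sets in the plural but shows one, and the body of Table 6.3: 1 and the ADS Plan cannot be read. A suitable set may exist there.

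The reply does not remove the core point. A listing gives no incidence and no denominator, and the visible rules exclude Visit 2 events from the tables by phase and, for non-randomised subjects, also by set.

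**Conclusion.** The point holds on the visible text, as a gap in ketamine safety reporting of low priority. Apart from events that worsen under study treatment, Visit 2 AEs are listed but not summarised. For each of the 36 planned randomised subjects, that is one of four infusions, and one of the two given without an active study drug. These counts assume the planned 36 subjects and three completed periods each.

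A reader might go further and infer that the tables will understate ketamine's risk, because subjects who tolerated Visit 2 badly may be among those never randomised. The documents give no Visit 2 event rate and no number of exposed but non-randomised subjects. Neither the direction nor the size of any difference can be stated, and no percentage should be claimed for that group.

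Randomised comparisons, the primary endpoint and the sample size are unaffected.

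**What to change.** - **SAP 6.3:** define a ketamine-exposed set of all subjects who received any ketamine, randomised or not.
- **SAP 6.1 and 7.8.1:** add one descriptive table of the number of subjects with AEs in the existing *Screening+Ketamine* window, on that set, split by randomised yes or no. Keep the Treated Set for every randomised-treatment table. In the same edit, reconcile the statement on treatment actually received with the rule that tables use analysing treatment.
- **Protocol 3.3.4 and SAP 6.6:** state that data of subjects who leave after ketamine only are entered and reported, in line with Protocol 5.2.6.2.1.

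**Cost:** one more subject set, one more table and a clarifying sentence. No new data are needed, since the AEs are already collected and the window is already defined. If the unseen Table 6.3: 1 or the ADS Plan already provides the set and table, a cross-reference and the wording alignment are enough.

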6.5 POOLING OF CENTRES

Data from both centers involved in this trial will be pooled.

6.6 HANDLING OF MISSING DATA AND OUTLIERS

CTP Section 3.3.4: “*If a subject is removed from or withdraws from the trial prior to the first administration of trial medication (BI 425809 or BI 409306 or lamotrigine or placebo) or ketamine, the data of this subject will not be entered in the case report form (CRF) and will not be reported in the clinical trial report (CTR). If a subject is removed from or withdraws from the trial after the first administration of trial medication, this will be documented and the reason for discontinuation must be recorded in the CRF; in addition, the data will be included in the CRF and will be reported in the CTR.*“

CTP Section 7.3: “*It is not planned to impute missing values.*”

One exception where imputation might be necessary for safety evaluation is AE dates. Missing or incomplete AE dates are imputed according to BI standards [\(3\)](#).

6.7 BASELINE, TIME WINDOWS AND CALCULATED VISITS

Due to the different analysing approaches with regard to the consideration of ketamine, baselines for pharmacodynamic and safety endpoints are defined separately.

[figure not shown]
On-ketamine analysis of CANTAB, [REDACTED] parameters (according to Section 2.2.2.2 of the CTP):

CTP Section 6.2.1: “*For the Screening Ketamine Challenge eligible subjects will come to the clinic in the morning of the test day, where they will participate in two assessment-sessions:*

- *Screening Baseline (= SCR BL)*
CANTAB tests, [REDACTED] will be done without any treatment, i.e. with no ketamine infusion
- *Screening Ketamine (= SCR KET)*
CANTAB tests, [REDACTED] will be done during ketamine infusion
[...]

The assessments of SCR KET will also be used as baseline for the assessments performed on the test days of the treatment periods, i.e. under treatments T1, T2, T3 and R.”

For the analysis of the pharmacodynamic endpoints (CANTAB tests, [REDACTED] two baselines exist. The pre-ketamine baseline is defined as the last non-missing value prior to start of ketamine infusion at screening. The during-ketamine baseline is defined as the first non-missing value during ketamine infusion at screening.

Safety analyses:

For safety analyses the baseline is defined as the last available value prior to administration of the respective treatment.

For ECG as well as vital signs a separate baseline can be defined for each treatment period as a pre-dose assessment on Day 1 (at Visit 3/4/5) is available.

Time windows are defined in Section 6.1 of the CTP. Adherence to time windows will be checked at the Report Planning Meeting.

